#### Missing data

##### *Part 2 analysis*

For Part 2 HINE motor milestones, Baseline will be retrieved from Part 1 and it will be the last assessment in Part 1.

Some general rules for the approaches to imputation of missing data are described in the following sections.

- 1) If a subject has any milestones missing at baseline then the missing milestone will be imputed using the median baseline value within the age of SMA onset ( $\leq 6$  months,  $>6$  months). for the correspondent milestone level
- 2) If a subject has any missing milestones at any visit that is not last visit, then the missing milestone will be imputed using a linear interpolation at the milestone level for any actual scheduled study visits.
- 3) If a subject has any missing milestones at last visit, then the missing milestone will be imputed using the lowest observed value for milestone assigned within the age of SMA onset ( $\leq 6$  months,  $>6$  months) and group to which the subject belongs at that visit (e.g., if a previous control subject's last visit is Day 120, then the at lowest observed value for the previous control group at Day 120 is used for the non-missing values for the specific motor milestone).

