16. STATISTICAL METHODS AND DETERMINATION OF SAMPLE SIZE

Part 1 and Part 2 will be analyzed separately. For Part 1, in general, continuous variables will be summarized by descriptive statistics, including number, mean, median, standard deviation, minimum, and maximum. Categorical variables will be presented with the number and percentage in each category. For Part 2, no formal statistical analyses will be performed. Descriptive statistics will be presented for safety and efficacy data collected.

For the Part 1 analysis, baseline is defined as the last nonmissing assessment prior to the first dose of study treatment in Part 1. For the Part 2 analysis, baseline is defined as the last nonmissing assessment prior to the first dose of study treatment in Part 2. In addition, a pooled analysis incorporating data from both Part 1 and Part 2 will be conducted to characterize the safety profile of Nusinersen. For subjects on active treatment in Part 1, safety data from both Part 1 and Part 2 will be included in the pooled analysis and the Part 1 baseline will be used for those subjects in the pooled analysis. For subjects on sham procedure in Part 1, only safety data from Part 2 will be included in the pooled analysis and the Part 2 baseline will be used for those subjects in the pooled analysis.

Concomitant medication usage for each subject will be listed for review.

The objectives of the study and the endpoints to be analyzed are listed in Section 6.

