#### **3.2 Demography and Baseline Disease Characteristics**

Baseline data (demography, birth characteristics and SMN history, medical history and baseline characteristics) will be summarized. Medical history was collected only at screening of Part 1.

Demography includes age at Part 1 first dose ( $\leq$ 7,  $>7\leq$ 18,  $>18$  months to 2 years,  $\geq$ 2 to  $<$  3 years,  $\geq$ 3 to  $<$ 4 years,  $\geq$ 4 to 5 years, and  $>5$  years) and age at Part 2 first dose (similar categories), sex, ethnicity, and race. SMA history will include age at SMA onset (months), age at SMA diagnosis (months), and disease duration.

Baseline disease characteristics will include HINE motor milestones and growth parameters – these assessments are further described in [Section 4](#).

Baseline will generally be defined as the closest measurement before the first dose/sham procedure. For Part 2, the baseline could be the predose assessment of Day 1, or the last assessment in Part 1, depending on the actual schedule of events in Part 2 see section 1.4.

Demographic and baseline disease characteristics will be presented for the Safety set as well as both repeated by age of SMA onset (< 6 months, >= 6 months).

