#### 4.5.1 HINE motor milestones

HINE Section 2 comprises eight tests for motor milestones: head control, sitting, voluntary grasp, ability to kick in supine position, rolling, crawling, standing, and walking.

There are 26 possible motor milestones that can be achieved using this schema (presented below). A subject whose results all appear in the first column (unable to maintain head upright, cannot sit, no grasp, etc.) has not achieved any motor milestone. A subject whose results all appear in the second column (head wobbles, sits with support at hips, uses the whole hand for a voluntary grasp, etc.) has achieved 8 motor milestones. A subject whose results all appear in the third column (head maintained upright all the time, props when sitting, index finger and thumb but immature grasp, etc.) has achieved 16 motor milestones.

*Attainment of motor milestones assessed by Section 2 of the Hammersmith Infant Neurological Examination (HINE)*

For the integrated analysis, the HINE motor milestones analyses will be presented by windowed analysis visits (see section 4.1).

The definition of a motor milestone responder is based upon the motor milestones categories in Section 2 of the HINE, with the exclusion of voluntary grasp as follows:

- Subject demonstrates at least a 2-point increase in the category of ability to kick or increase to the maximal score on that category (touching toes), or a 1-point increase in the motor milestones category of head control, rolling, sitting, crawling, standing, or walking AND
- Among the motor milestone categories, with the exclusion of voluntary grasp, there are more categories where there is improvement, as defined in (i) below, than there are categories where there is worsening (as defined below).
- Subjects who die or withdraw from the study on or prior to the visit will be counted as non-responders and will be included in the denominator

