Improvement in motor milestones is defined as a 2-point increase in the total motor milestones score, where voluntary grasp is excluded. For example, (i) a 1-point increase in head control and a 1-point increase in rolling is considered a response, (ii) a 2-point increase in rolling is considered a response, (iii) a 2-point increase in rolling with a 1-point decrease in head control is considered a non-response. Worsening is defined as at least a 2-point decrease or a decrease to the lowest possible score of no kicking. For the other 6 categories, worsening is defined as at least 1-point decrease.

To illustrate this responder definition, examples are provided below. In these examples, it is assumed that there are no changes in motor milestone categories other than those stated.

- A subject with a 2-point increase of ability to kick, a 1-point increase in rolling, and a 1-point decrease in head control is a responder.
- A subject with a 1-point increase of ability to kick from “touches legs” to “touches toes” is a responder.
- A subject with a 1-point increase of head control and a 1-point decrease rolling is a non-responder.
- A subject with a 1-point increase of rolling and a 2-point decrease in ability to kick is a non-responder.
- A subject with a 1-point increase of rolling and a 1-point decrease of ability to kick from “upward vertically” to “kicks horizontal, legs do not lift” is a responder.
- A subject with a 1-point increase of rolling and a 1-point decrease of ability to kick from “kicks horizontal, legs do not lift” to “no kicking” is a non-responder.
- A subject with a 2-point increase of voluntary grasp is a non-responder.
- A subject with a 1-point increase of rolling and a 2-point decrease of voluntary grasp is a responder.

The response will be conducted on data from each visit and windowed visit separately for Part 2 and integrated analysis respectively (see section 4.1 for details about the windowing).

*Additional presentations of HINE motor milestones*

- The above responder analysis will be repeated for the subjects that are responder at last available assessment. For those subjects that are responders, the analysis visits when first respond occurred will be also displayed.
- The proportion of subjects who have achieved the follow milestones:
  - Full head control,
  - Stable sit or pivots,
  - Stand unaided,
  - Walk independently
 will be presented by visit and at the last available assessment (for the integrated analysis)

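### A HINE item missing at the Part 2 baseline is filled with an onset-stratum median instead of the child's own last Part 1 score, which can flip individual response calls

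*SAP*

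**What the plan says.** SAP Section 4.5.1, Missing data, Part 2 analysis, sets the HINE baseline: "Baseline will be retrieved from Part 1 and it will be the last assessment in Part 1". Rule 1 covers an item missing at that visit: "the missing milestone will be imputed using the median baseline value within the age of SMA onset". The strata are onset at 6 months or earlier and onset after 6 months. Rule 1 does not mention treatment group. Rule 3 in the same list, for an item missing at the last visit, does: "and group to which the subject belongs at that visit". No rule lets the child's own earlier score stand in for a missing baseline item.

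Protocol Section 16 states: "For the Part 2 analysis, baseline is defined as the last nonmissing assessment prior to the first dose of study treatment in Part 2". SAP Section 3.2 is looser: "For Part 2, the baseline could be the predose assessment of Day 1, or the last assessment in Part 1".

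HINE is scheduled in Part 1 on Day 1 predose, Days 64, 183 and 302, and End of Part 1 (Protocol Table 2). It is not scheduled on Part 2 Day 1 (Protocol Tables 3 and 4).

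Response under Section 4.5.1 can be triggered by "a 1-point increase in the motor milestones category of head control, rolling, sitting, crawling, standing, or walking", provided that "there are more categories where there is improvement" than categories with worsening. Ability to kick has its own thresholds and voluntary grasp is excluded. On worsening: "For the other 6 categories, worsening is defined as at least 1-point decrease".

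The integrated analysis repeats rule 1. Under SAP Section 2, previous-nusinersen children are followed there from their first Part 1 dose, and one column follows previous controls from their first Part 2 dose.

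**The concern.** A stratum median is a defensible fill-in at randomisation, because the arms are then exchangeable and no earlier score exists. Neither holds at entry to Part 2. The groups have had different treatment for a Part 1 planned at about 14 months. SAP Section 2 adds that sham children left Part 1 first, regardless of planned dosing days, so length of follow-up can differ too. The Part 2 results are then displayed by these same groups.

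If nusinersen children score higher by then, a pooled median tends to be too high for a previous-sham child, which hides gains, and too low for a previous-nusinersen child, which invents them. The baseline enters every later visit, so one wrong value feeds the responder table, the change scores, the plots and the onset-stratum summaries throughout Part 2.

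**Working it through.** **1. Reproduce the plan's rule.** The responder rule was coded by category: a gain of 1 in any of six items, or a gain of 2 or reaching the maximum for kick; improved categories must outnumber worsened ones; grasp excluded. It returns the SAP's answer for all eight worked examples in Section 4.5.1 (4 responders, 4 non-responders).

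**2. Enumerate one missing item.** Let b be the true baseline, f the follow-up score and m the imputed baseline, with all other items unchanged. The true call is response if f − b ≥ 1; the reported call is response if f − m ≥ 1. For follow-up score f on an item scored 0 to K, f baseline values lie below f and K + 1 − f do not. Hidden responses and false responses therefore each number Σ f(K + 1 − f).

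- K = 2: 1×2 + 2×1 = 4 of each, so 8 wrong calls of 3³ = 27.
- K = 3: 1×3 + 2×2 + 3×1 = 10 of each, so 20 wrong calls of 4³ = 64.

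These count possible combinations; they are not probabilities.

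**3. A worked stratum (assumed scores).** Sham 0, 0, 1; nusinersen 1, 1, 2, 2, 2, 2. The pooled median is 1, the sham median 0 and the nusinersen median 2.

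- A previous-sham child truly at 0 who reaches 1 is a responder on the own score; against 1 the change is 0 and the response is hidden.
- A previous-nusinersen child stable at 2 shows 2 − 1 = +1, a false response.
- A previous-sham child who gains 1 in rolling and stays at 0 in head control (missing at baseline, imputed 1) shows a false worsening that cancels the real gain.

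With an even number of values the median can be 1.5, and a later score of 2 then misses the 1-point threshold.

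**4. Illustrative simulation.** Assumptions: item scored 0–3, SD 0.9; nusinersen children 1 point higher at Part 2 entry; true gain probability 40% (sham) and 30% (nusinersen); stratum sizes (sham + nusinersen) from 2+5 to 5+9. For the own earlier score, 20% of nusinersen children had risen, and 10% of sham children had fallen, by 1 point since that visit. False rates are among true non-responders and hidden rates among true responders, per child with the item missing.

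| Baseline used | Sham: false | Sham: hidden | Nusinersen: false | Nusinersen: hidden |
|---|---|---|---|---|
| Pooled stratum median | 9–13% | 64–74% | 41–48% | 29–37% |
| Stratum-and-group median | 26–35% | 34–45% | 29–32% | 49–54% |
| Own earlier score | 0% | 10–11% | 19–20% | 0% |

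With no group difference the pooled median still gives 28–33% false and 30–38% hidden. Replacing a child's score by any median produces much of the error; pooling mainly tilts its direction by group.

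**5. Weight of one child.** At the planned 7 and 14 children, one changed call moves a responder proportion by 100/7 = 14.3 or 100/14 = 7.1 points.

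**The case against.** A reader might infer that the SAP contradicts the protocol's baseline. At visit level it does not. No HINE is scheduled on Part 2 Day 1, so the last Part 1 HINE is the last one before the first Part 2 dose. The gap is narrower: whether last means last nonmissing for each item. If that was intended, rule 1 would reach only items never scored in Part 1; the SAP does not say so.

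A reader might also extend the bias to the whole integrated analysis. Previous-nusinersen children there use the pre-treatment Part 1 baseline, so divergent Part 1 treatment cannot distort it. Only the column following previous controls from their first Part 2 dose is exposed. For those children the SAP keeps the two periods separate and bars interpolation between them, which any correction must address.

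Third, it is tempting to blame pooling alone and add group to the median. The table shows that this does not cure the error. Suppose, for example, that nusinersen scores are 0, 1, 1, 2, 2, 2, 3, 3, 3. The group median is 2, and a child stable at 3 still shows a false +1.

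Fourth, the own earlier score has its own bias. Part 1 HINE visits are about four months apart after Day 64, so an earlier score can be too low in an improving child. The 19–20% false rate for nusinersen largely reflects the assumed 20% who had changed. That objection stands as a cost of the fix.

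Finally, response is judged over seven categories, so one wrong item changes the call only when the others do not settle it. Early termination of Part 1 also means some later own scores will not exist, although the Day 1 score precedes any early stop.

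**Conclusion.** The concern holds as a possibility. Followed as written, rule 1 can create false responses and hide true ones in the Part 2 HINE summaries and in the integrated column for previous controls in Part 2. Severity is minor to moderate.

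The conclusion rests on three readings. Pooling across groups is inferred from rule 1 naming only the onset stratum while rule 3 adds group. The last assessment is read as a visit, not item by item. The response rule is read by category; Section 4.5.1 also describes improvement as a 2-point rise in total score, and under that wording a lone 1-point error would not by itself make a response.

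The documents give no count of missing baseline items and no stratum sizes, so the actual effect is unknown and the simulated rates are not forecasts. A reader might infer that a main trial conclusion is at risk. The documents do not support that: HINE is exploratory, Part 2 is descriptive with no formal analysis, and the primary endpoints are safety.

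**What to change.** In SAP Section 4.5.1, define the Part 2 HINE baseline item by item as the child's last nonmissing score before the first Part 2 dose. This agrees with Protocol Section 16. Apply it to the Part 2 analysis and to the integrated column for previous controls in Part 2, and state in the integrated section that using the child's own observed Part 1 score as baseline is not the interpolation between periods that the section bars.

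Keep a median only for an item never scored in Part 1, and state which children's values enter it. List every imputed or carried-forward baseline item with the visit it came from, and repeat the responder summary without them.

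The cost is a few sentences, minor programming, one listing and one repeated table; no new data are needed. The remaining drawback is the possibly stale score in improving nusinersen children, which the listing and the repeated table make visible.

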##### *Integrated analysis*

For the integrated analysis, these rules will be applied:

For subjects randomized to Nusinersen in Part 1 then Part 1 and Part 2 will be considered as a one period and any data available will be used for any imputation. However, for subjects who were randomized to receive Sham in Part 1 then the two periods (Part 1 and 2) will be considered separately and no imputation will be allowed i.e., no interpolation between the 2 periods.

The imputation of missing data will follow these rules:

- 1) If a subject has any milestones missing at baseline then the missing milestone will be imputed using the median baseline value within the age of SMA onset ( $\leq 6$  months,  $>6$  months). for the correspondent milestone level
- 2) If a subject has any missing milestones at any other visit that is not last visit then the missing milestone will be imputed using a linear interpolation at the milestone level for any actual scheduled study visits (for last visit, please see bullet point 4).
- 3) Perform windowing selecting the closest non-missing milestone to the target date
- 4) If a subject has a least one milestone observed but some milestones are missing, then any missing milestones at the last visit will be imputed using the lowest observed value for that milestone, assigned within the age of SMA onset ( $\leq 6$  months,  $>6$  months) to which the subject belongs, at that windowed analysis visit. If only a date is available and all of the milestones are missing, then no imputation will be performed.

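### A HINE item missing at the last visit is filled from other children's scores with no cap at the child's own, so a small cell can create a response the child never showed

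*SAP*

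**What the plan says.** SAP section 4.5.1, Missing data, gives separate rules for the two analyses.

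- **Part 2, rule 3.** The trigger is "If a subject has any missing milestones at last visit". In that case "the missing milestone will be imputed using the lowest observed value for milestone", taken within a cell defined by onset stratum "and group to which the subject belongs at that visit". The illustration supposes what happens "if a previous control subject's last visit is Day 120".
- **Integrated, rule 4.** If at least one item was observed, "any missing milestones at the last visit will be imputed using the lowest observed value for that milestone". The cell here is onset stratum by windowed visit; Part 1 group is not part of it.
- **Part 2 baseline.** "Baseline will be retrieved from Part 1 and it will be the last assessment in Part 1", so change is measured against the child's own history.
- **Responder definition (4.5.1).** One route is "a 1-point increase in the motor milestones category of head control, rolling, sitting, crawling, standing, or walking", provided more categories improve than worsen. Kicking needs a 2-point rise or a rise to its maximum. Voluntary grasp does not count.
- **Use.** Response is analysed at each visit and again at the last available assessment. Total score and change from baseline are also presented.
- **Visits.** SAP sections 1 and 2 say that all children leave Part 2 early for the extension study and that actual study days vary widely. Section 4.1 relabels a Part 2 end visit as unscheduled if it is more than 7 days from a scheduled one.

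**The concern.** Taking the lowest value in a cell looks conservative. It is so only if at least one donor scores no higher than the child whose item is missing. That child cannot be a donor, because the item is missing at that visit. If every donor is stronger, the fill sits above anything the child has shown and counts as improvement.

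The cells are likely to be small. Protocol section 7.1 plans up to 14 nusinersen and 7 sham children, and Part 2 rule 3 divides these by onset and visit. An end visit relabelled as unscheduled may have no matching cell, and no rule covers an empty one. The SAP's illustration shows the difficulty: Day 120 is a visit of the previous-nusinersen group and is not on the previous-control schedule.

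At stake is the responder status of individual children. With the planned numbers, one changed child moves a responder proportion by 1/7 = 14.3 percentage points among previous controls, or 1/14 = 7.1 among previous nusinersen children.

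**Working it through.** The plan has no figure to reproduce: SAP section 8 says there are no formal sample size calculations. The check is therefore on the logic of the rule.

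**1. Responder rule.** Coded as defined in 4.5.1, it agrees with all eight bulleted examples there. The same section also carries a sentence defining improvement as a 2-point rise in total score without grasp. That sentence disagrees with three of the eight examples (the second, fifth and eighth), so both wordings are shown below.

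**2. Worked cells under Part 2 rule 3.** A child has rolling = 0 at baseline and at every observed visit. Rolling is missing at the last visit and nothing else changes.

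| Donor scores | Fill | 1-point rule | 2-point-total wording | Fill capped at own score |
|---|---|---|---|---|
| 1, 2, 2 | 1 | responder | non-responder | 0, non-responder |
| 2, 3 | 2 | responder | responder | 0, non-responder |
| 2 | 2 | responder | responder | 0, non-responder |
| 0, 2, 3 | 0 | non-responder | non-responder | 0, non-responder |

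A response can therefore be created, and a fill 2 points above the child's score creates one under either wording.

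**3. Illustrative size of P(fill > own score).** The documents give no score distribution. Assume independent scores, uniform on 0 to k, with m donors. The ranges k = 3 and k = 4 fit eight items totalling 26 milestones (6 × 3 + 2 × 4 = 26). Then

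P = sum over s = 0..k of [1/(k+1)] × [(k − s)/(k+1)]^m.

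For k = 3:
- m = 1: (3+2+1+0)/16 = 0.375
- m = 2: (9+4+1)/64 = 0.219
- m = 3: (27+8+1)/256 = 0.141
- m = 6: (729+64+1)/16384 = 0.048

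For k = 4 the same sum gives 0.400, 0.240, 0.160 and 0.063.

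**4. Sensitivity to the assumption.**
- If every donor has gained 1 point (up to the maximum), the probabilities for 1, 2, 3 and 6 donors become 0.56, 0.43-0.45, 0.36-0.39 and 0.26-0.30.
- For a child at 0, P = (1 − f)^m, where f is the share of donors at 0. With m = 3 and f = 0.10, 0.25, 0.50 and 0.75, P = 0.729, 0.422, 0.125 and 0.016.

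The result depends heavily on how many donors there are and how many of them score 0.

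**5. From fill to response.** A changed status also needs the item to be missing at the last visit, a fill far enough above baseline for that item, and a child who is not already a responder and whose improved categories then outnumber the worsened ones. The documents give no rate for any of these.

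**The case against.** The strongest reply concerns size and scope, since the text plainly sets no cap. HINE assessment is scheduled at the Part 2 final or early termination visit, so ending Part 2 early does not by itself make items missing. Children who die or withdraw are already counted as non-responders. Visits before the last are filled by interpolating the child's own data. Integrated rule 4 draws on both groups, on windows of about 120 days after Day 64, and requires an observed item, so its cells should be larger. The protocol's account of untreated disease (section 5.1) describes Type I children as never sitting or walking, which suggests scores near the floor, and a single donor at 0 brings the fill to 0. HINE is exploratory, and Part 2 has no formal analysis.

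All of this stands, and it limits the point without removing it. Moving to the extension study is the planned end for every child and is not described as non-response, so the non-responder rule does not clearly cover those children. Larger cells make an upward fill less likely but still disregard the child's own scores.

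A reader might infer that some 38% of children with a missing item would be turned into responders. The documents do not support that. The figure is the chance that the fill exceeds the child's own score, with one donor and an assumed distribution.

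**Conclusion.** The point holds as a defect in an exploratory analysis. Part 2 rule 3 can give a child with unchanged ability a gain that meets the responder definition, and it has no answer for an empty cell. Integrated rule 4 shares the first weakness to a lesser degree. The mechanism follows from the text alone and needs no distributional assumption. Its frequency cannot be known from the documents. The figures of 38-40% with one donor and 5-6% with six rest on uniform, independent, unchanged scores; they fall if donors cluster at 0 and rise if donors have improved. The shifts of 14.3 and 7.1 points use the planned maxima, whereas the denominators are set visit by visit.

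A reader might also infer that the rule biases HINE response upward overall. That is not shown either. A weaker donor pulls the fill below the child's own score and can cancel a true response, and adding donors can only lower the minimum. No test or decision in the plan rests on HINE response, so the change is worth making but not critical.

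**What to change.** In both the Part 2 and the integrated rules, fill an item missing at the last visit with the lower of the child's own last observed score for that item and the cell minimum. If the cell has no donor, including when the end visit was relabelled as unscheduled, use the child's own last observed score. A filled item can then never exceed what the child last showed.

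Add a table of HINE response and total score on observed data only, because the cap does not remove false losses caused by a weaker donor. Replace Day 120 in the illustration with a visit on the previous-control schedule.

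The cost is about one SAP sentence for the rule, one additional table and a corrected example. A true late gain in a missing item is not credited, and downward fills remain.
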